TITLE PAGE

Full protocol title: Addressing Disparities in Neuromodulation for Rehabilitation: A Mixed Methods Approach to Optimize Access for Underrepresented Racial Minorities

Protocol Version Date: **12/16/2023**

PI Name: **[name]**

NCT Number: NCT05896202

1) Protocol Title

Addressing Disparities in Neuromodulation for Rehabilitation: A Mixed Methods Approach to Optimize Access for Underrepresented Racial Minorities

2) IRB Review History*

Approved (ID 20230154)

3) Objectives*

We will develop culturally sensitive videos for video-enhanced informed consent (VE-IC) with neuromodulation techniques (i.e., vagus nerve [taVNS] and transcranial magnetic [rTMS] stimulation techniques). We will use these videos in a mixed method study design to examine factors that influence the interest or aversion to participate in neurostimulation research in URM with persistent pain. Findings will provide insight on modifiable factors and recruitment/retention strategies to optimize racial minority representation in neurostimulation research. The videos and data from this project will be used in our future research on neurostimulation, and they will be made available for use by others. This study is part of a larger research agenda designed to inform the development of personalized pain relief programs based on using patient preferences and a mechanistic understanding of the interventions to integrate neurostimulation interventions into multimodal care for persistent pain.

Aim 1: Development of culturally sensitive videos for enhance informed consent with neurostimulation and determination of factors that influence minority interest in participating in neurostimulation research. *We hypothesize that participants will have greater interest in participation and expectations for pain relief with the modality for which they received VE-IC in comparison to modalities without VE-IC.*

Aim 2: Examination of the influence that video enhanced informed consent has on expectations with taVNS and on treatment intended effects. *We hypothesize that individuals who had VE-IC for taVNS will demonstrate greater expectations for pain relief and greater changes in heart rate variability (HRV).*

Aim 3: Explore the intended effects of taVNS in people with neuropathic pain. The sample consent form and brochure for taVNS will not specify the exact location on the ear for active taVNS. Thus, participants in the TMS video only group will be sufficiently naïve for participation in a single blinded crossover design. Half of the TMS-only group will receive active taVNS in visit 2, the other half will receive sham taVNS in visit 2, and they will crossover for visit 3 (table 1). *We hypothesize that there will be a greater increase in HRV and SICI with active taVNS than with sham taVNS.*

4) Background*

Noninvasive neurostimulation techniques show promise for improving chronic pain management.¹⁻³ Underrepresented racial minorities (URM) are at greater risk than non-minority individuals for persistent pain conditions⁴⁻⁶; however, recruiting URM for adequate representation in neurostimulation research remains an unmet challenge. Improving recruitment of URM participants in neurostimulation research

is critical to enhancing our understanding of factors that influence outcomes with these modalities and to maximize the generalizability of research findings to a diverse population.

Traditional consent forms have been criticized for being too long and difficult to understand, and these consent forms may be a barrier to URM participation in research, as limited literacy disproportionately affects URM and the text heavy format may foster distrust. Video-enhanced informed consent (VE-IC) has been recommended to improve recruitment of URM in cancer and cardiovascular trials; however, VE-IC has not been studied in neuromodulation research.

5) **Inclusion and Exclusion Criteria***

We anticipate that most participants in this study will have chronic pain associated with chemotherapy induced peripheral neuropathy (CIPN); however, we will recruit Black and Hispanic people with chronic neuropathic pain of any etiology (e.g., diabetic neuropathy and radiculopathy) to optimize the rapid recruitment of these URM.

Inclusion Criteria: 1) between the ages of 18-80 years; 2) neuropathic pain lasting longer than 3 months (i.e., complaint of sensation of burning, stabbing or pressing pain, shooting or shock like pain, or paresthesias); 3) Neuropathic Pain Symptom Inventory score ≥ 10 . 4) self identifies as Black or Hispanic

Exclusion Criteria: 1) any unstable medical condition or medical contraindication to moderate physical exertion (e.g., unstable angina or cardiac arrhythmia), 2) pregnancy, 3) currently taking Buprenorphine or recently stopped taking (within 1 month), 4) presence of cognitive impairment or language barrier that impairs full autonomy in the consent process or in the ability to participate in detailed interviews, 5) implants in the head or neck, cochlear implants, or pacemaker, 6) head or neck metastasis or recent ear trauma, 7) history of seizures.

6) **Study-Wide Recruitment Methods***

All recruitment will be in accordance with the Health Insurance Portability and Accountability Act (HIPAA), by the SCCC Protocol Review and Monitoring Committee and by the UM Department of Physical Therapy Research Leadership Team.

Black and Hispanic patients with persistent pain will be recruited for a 2-phased mixed methods study. Flyers will be placed in Uhealth clinics (Uhealth Physical Therapy, Uhealth Advanced Pain Management Center, and Sylvester Comprehensive Cancer Center) to recruit patients with neuropathic pain. In addition, the patient census of specific UHealth clinics (i.e., [name] medical oncology clinic, the Sylvester Posner Lymphema Clinic, and the Uhealth Pain Physical Therapy Clinic) will be used for recruitment. *Physicians will be informing participants first about the study before a member of the study team will be contacting patients.* Telephone numbers and/or emails of potential participants and they will be called to screen for inclusion. Patients who provide verbal consent to be

contacted for research purposes will be called by one of the research assistants.

The Sylvester Behavioral and Community-Based Research (BCSR) Shared Resource will be used to assist with recruitment of patients with chemotherapy induced peripheral neuropathy (CIPN).

7) Study Design

Primary Purpose: Other. This study will utilize principles of community-based participatory research to develop and test educational materials for consenting people to neurostimulation research.

Study Phase: N/A

Interventional Study Model: Parallel

Number of Arms: 2

Masking: Subject only

Allocation: Randomized

Enrollment: 28

8) Study Timelines*

Each participant will complete 3 visits for a total of ~10 hours, and it is expected that the visits are completed within 1-2 weeks of each other. Thus, participants will be enrolled for less than 3 weeks on average.

9) Study Endpoints*

Primary Outcome Measure Title: Change in Heart Rate Variability (HRV)

Primary Outcome Measure Description: HRV will be measured with an H10 chest strap device (Polar, Finland)

Primary Outcome Measure Timeframe: at visits 2 and 3, Baseline (15 minutes pre taVNS application) to 15 minutes post 1 hour application of taVNS

Secondary Outcome Measure Title: Change in EXPECT questionnaire scores

Secondary Outcome Measure Description: scores ranging from 0-40 with higher scores representing greater expectations for pain relief

Secondary Outcome Measure Timeframe: at visits 2 and 3, Baseline (pre taVNS application) and repeated post 1 hour application of taVNS

10) Arms and Interventions

All participants will be educated on both neurostimulation modalities (taVNS and TMS). This study will include 2 arms. Group 1 will receive a supplemental video on taVNS, in addition to consent forms and brochures describing both modalities.

Group 2 will only receive the consent forms and brochures describing both modalities. While all participants will provide important feedback on consent forms and brochures for both modalities, Group 1 will provide additional feedback specific to the taVNS video they watched.

We will assess the impact of the taVNS video (by comparing Group 1 to Group 2) on participant expectations and intended effects with a single 60-minute bout of taVNS.

11) Procedures Involved*

Black and Hispanic patients with persistent pain will be recruited for a 2-phased mixed methods study. All data collection will take place at the Lynn Rehabilitation Center. In the first phase, participants will be educated on two neurostimulation modalities (taVNS and TMS).

Educational materials will include 1:1 discussion of a typical consent form for each modality, a brief (2 page) description with pictures for each modality, and the brief video for taVNS for those randomly allocated to Group 1. *The development of these educational resources is a primary objective of this project, and the first few months will be spent consulting with experts to develop these educational resources and to produce the videos.*

Structured interviews and questionnaires will be used to examine participants interest in participating in research for each of the modalities, gather their feedback on each educational tool, and to determine factors that influence their interest. This first phase will take place in a single session, and the session is anticipated to take ~2 hours to complete.

Participants will be given the choice to complete this first visit in person or via Zoom in order to decrease participation burden. For the second phase, all participants will receive active taVNS, but only Group 2 will receive both active and sham taVNS in a randomized crossover design.

All participants will first complete a pretrial assessment battery, followed by a 60-minute trial of taVNS applied with continuous monitoring of HRV during quiet sitting, and then concluded with a posttrial assessment. The second phase will be completed in two sessions that are anticipated to last ~4 hours each. In summary, participants will complete 3 visits for a total of ~10 hours to complete the study.

	Visit 1	Visit 2	Visit 3
taVNS video (n=12)	Education and baseline	Active taVNS	1-wk follow up
Brochures only (n=12) 6 participants	Education and baseline	Active taVNS	Sham taVNS
6 participants	Education and baseline	Sham taVNS	Active taVNS

A detailed description of each procedure is provided below:

*EXPECT questionnaire*⁷: The EXPECT is a 4-item questionnaire that assesses expectations for pain improvement. Each of the 4 items is scored on an 11-point scale, with 0 being no change and 10 representing complete relief. It is anticipated that this questionnaire will take less than 5 minutes to complete.

Heart rate variability (HRV): HRV will be measured with an H10 chest strap device (Polar, Finland) and will serve as the primary endpoint for response to taVNS in Aim 2. Participants will wear the chest strap continuously throughout the application of taVNS.

taVNS: A portable taVNS Stimulator (Soterix Medical, Woodbridge, NJ) will be used with flexible hydrogel electrodes to administer taVNS at the cymba concha (Figure 2), using monophasic pulses (pulse width:500 μ s; frequency 10 Hz), and delivered up to 200% of the perception threshold, but kept below the pain threshold, for 60 minutes. This device is approved for research purposes, and these parameters have been shown to maximize cardiovagal response with taVNS.⁸ Participants will be quiet sitting in a comfortable chair during the application of taVNS.

Figure 2. taVNS electrode application

Please see the Risks to Subjects section for procedures performed to lessen the probability or magnitude of risks.

12) Data Management*

The principal investigator will be responsible for all data management and analyses. A research assistant will assist with data entry and qualitative data coding. All quantitative data will be entered and stored in the University of Miami REDCap system. NVivo 12 software (QSR International, United States) will be used for qualitative data management and analyses, and SPSS version 28 (IBM, United States) will be used for quantitative analyses (i.e., descriptive statistics).

13) Provisions to Monitor the Data to Ensure the Safety of Subjects*

Safety information will be collected during the taVNS trial study visit for this research and entered into Velos for tracking. All adverse effects will be reported to the study team, the IRB, and to the SCCC Data & Safety Monitoring Committee. All research activities will be stopped in the case

of a single serious adverse reaction (i.e., seizure) or if 3 or more minor adverse reactions (e.g., skin irritation from electrodes) are observed. A corrective plan (e.g. change in TMS or taVNS protocol) must be approved by the study team, IRB, and SCCC Data & Safety Monitoring Committee before research activities can be resumed.

The plan might include establishing a data monitoring committee and a plan for reporting data monitoring committee findings to the IRB and the sponsor.

14) Community-Based Participatory Research*

Prior to initiating research activities, a 4-member community advisory board (CAB) will be assembled, consisting of 2 people from each ethnicity (non-Hispanic African American and Hispanic), and the CAB will meet 4 times over the course of the year to provide general feedback on the project design, plan, and progress, including feedback on video scripts, final video products, and video dissemination plan. At least 1 person from each ethnic group on the CAB must have chronic pain (n≥2).

15) Sharing of Results with Subjects*

NA

16) Setting

Participants will be recruited from Sylvester Comprehensive Cancer Center, UHealth Physical Therapy, and from the UHealth Advanced Pain Management Clinic.

The research procedures will be conducted at the Lynn Rehabilitation Center for The Miami Project to Cure Paralysis at UHealth/Jackson Memorial. The Christine E. Lynn Rehabilitation Center for The Miami Project to Cure Paralysis at UHealth/Jackson Memorial was designed from scratch to be one of the country's elite facilities for patients recovering from traumatic brain injury, spinal cord injury, cancer treatment, and other complex conditions. The stunning 250,000-square-foot, nine-story structure opened in 2020, and it houses 80 inpatient beds and features world-class amenities and next-generation rehabilitative technology.

Every aspect of the facility underscores a focus on comprehensive care. The building's layout ensures that clinical care and research share space, so that patients and families see the scientists who are developing treatments, and researchers interact with real people who need the results of their work—a constant reminder of the way Lynn Rehabilitation Center integrates academic study with the day-to-day treatment of patients.

[name] Pain Research Lab is located in the Lynn Rehabilitation Center. His dedicated lab space is equipped with a PC, laptop, secured internet access, filing cabinets, office and medical supplies, and research equipment and supplies.

A community advisory board will be formed to provide feedback and guidance on the videos produced as part of this research. Please see details in the Community-Based Participatory Research section.*

17) Resources Available

Research Team:

[name], DPT, PhD

Principal Investigator

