There are no direct costs associated with participating in this study. However, transportation and parking may be an economic burden on some participants. Participants will be paid \$250 to compensate them for the economic and time burden (\$50 upon completion of visit 1 and \$200 for completion of visit 2).

23) Consent Process

We will follow SOP: Informed Consent Process for Research (HRP-090). The consent process will begin with the phone screening. If they provide verbal consent to the phone screening and are deemed eligible for the study, then they will be invited to the Lynn Center. At the Lynn Center, they will be educated on the study and provided with a written consent form to review and sign. The consent form and all research documents will be available in English and Spanish. Several of the research team members are bilingual and each participant will be consented in-person in the language which they are most comfortable. Potential participants will have the opportunity to consult with family members or others and will have all questions addressed by the PI or other members of the study team. Potential participants will be briefed on their rights as a research subject, including their right to withdraw at any time with no negative consequences.

The study procedures will be reviewed with each participant at each phase of the study (i.e., tVNS and TMS procedures will be reviewed after completion of the mixed methods phase and prior to initiating the trial phase) and verbal consent will be re-obtained to ensure ongoing consent.

Each time that the verbal consent is obtained, it will be reiterated to the patient that they may choose to withdraw from the study at any time.

Non-English-Speaking Subjects

All study documents will be available in English and Spanish. A bilingual study team member will be present at all times to answer any questions and to ensure that Spanish speaking participants fully understand. As noted previously, each participant will be consented in-person in the language which they are most comfortable.

e-Consent

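### Do the undescribed SICI outcome in Aim 3 and the enrolment of 28 against 24 in the visit table call for a change to the plan?

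*Combined protocol and SAP*

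**What the plan says.** Aim 3 (Section 3) states the hypothesis of a "greater increase in HRV and SICI with active taVNS than with sham taVNS". The comparison is a single-blind crossover within one group.

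Section 9 lists two outcomes. The primary is change in HRV, timed "at visits 2 and 3, Baseline (15 minutes pre taVNS application) to 15 minutes post 1 hour application of taVNS". The other is given as "Secondary Outcome Measure Title: Change in EXPECT questionnaire scores".

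Section 11 says of the second phase: "All participants will first complete a pretrial assessment battery". Stimulation and a post-trial assessment follow. The contents of these assessments are not listed. The section then announces: "A detailed description of each procedure is provided below". The entries that follow are EXPECT, HRV and taVNS.

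On numbers, Section 7 gives enrolment of 28 in two randomised arms and the study model as *Parallel*. The visit table in Section 11 shows 12 in the video group and 12 in the brochures-only group, the latter split 6 and 6 by order of active and sham stimulation.

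Two other places mention TMS as if it were applied in the study. Section 13 gives as an example of a corrective plan a "change in TMS or taVNS protocol". Section 23 says that "tVNS and TMS procedures will be reviewed after completion of the mixed methods phase and prior to initiating the trial phase".

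**The concern.** A hypothesis that names an outcome should lead the reader to a measurement, a time point and a direction of effect. For SICI the available text supplies none of these, beyond the word increase in the hypothesis itself. If SICI is not collected, half of the Aim 3 hypothesis cannot be examined. If it is collected, its measure and timing have not been fixed in advance, which leaves room for choice after the data are seen.

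The two sample-size figures raise a second doubt. A reader who later sees 24 analysed cannot tell whether that is the full planned sample or a sample that lost 4.

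The labels add to the impression of a text only partly updated. Aim 3 places the crossover in a group that saw a TMS video, whereas Sections 10 and 11 place it in Group 2, which sees no video. The study model in Section 7 does not mention a crossover at all.

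**Working it through.** **1. Outcomes against measures.** The three aims hypothesise four distinct outcomes.

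| Outcome | Aim | In Section 9? | Described measure |
|---|---|---|---|
| Interest in participating | 1 | No | Interviews and questionnaires (Section 11) |
| Expectations | 1, 2 | Yes | EXPECT, 0 to 40 |
| HRV | 2, 3 | Yes | Chest strap, pre and post stimulation |
| SICI | 3 | No | None found |

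SICI is therefore the one outcome of four with no described measure. The entry for interest rests on this sentence: "Structured interviews and questionnaires will be used to examine participants interest in participating in research for each of the modalities". It names no instrument or scale. HRV has a device and a time frame but no named HRV index. The contrast with SICI is real but narrower than a count of 3 against 1 suggests.

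**2. Is the Section 11 list complete?** Three things the trial does have no entry of their own in it:
- sham taVNS, which is in the visit table;
- the Neuropathic Pain Symptom Inventory, which Section 5 requires for inclusion;
- the structured interviews, which are mentioned only in the narrative.

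Absence from the list is therefore weak evidence that something is not done.

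**3. Is there time for an unlisted assessment?** Section 11 allows about 4 hours, or 240 minutes, for each second-phase session. The itemised content is:
- stimulation: 60 minutes;
- HRV before and after, reading the Section 9 time frame as two windows: 15 + 15 = 30 minutes;
- EXPECT twice, at under 5 minutes each: at most 10 minutes.

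The total is 60 + 30 + 10 = 100 minutes, leaving about 240 − 100 = 140 minutes for set-up and the un-itemised assessments. That is ample room, though it does not prove that SICI is among them.

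**4. Would the analysis change?** Section 12 describes the quantitative analysis as descriptive statistics. No hypothesis test, alpha or power is given for any aim in the available text. No planned test, error rate or sample-size calculation therefore depends on whether SICI stays or goes.

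**5. Enrolment of 28 against 24.** The table total is 12 + 6 + 6 = 24, and 28 − 24 = 4. That is 4/28 = 14.3% of those enrolled. The documents give no derivation of 28, so it cannot be reproduced. Several unstated assumptions reach it:
- 10% loss, rounding up in each arm: 12/(1 − 0.10) = 13.3, so 14 per arm and 28 in total;
- 12.5% loss overall: 24/(1 − 0.125) = 27.4, so 28;
- 14.3% loss overall: 24/(1 − 1/7) = 28;
- counting the 4-member community advisory board of Section 14: 24 + 4 = 28.

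Not every allowance gives 28. A 10% loss applied to the total gives 24/0.90 = 26.7, so 27; a 15% loss gives 24/0.85 = 28.2, so 29. The figures are compatible, but the documents do not say which account is meant.

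**6. Labels.** Aim 3 describes a group in which half receive active stimulation first and half sham first, crossing over at visit 3. Only the brochures-only group in the visit table, split 6 and 6, fits. The group is identifiable despite the wrong name. The two randomised arms are indeed parallel, and Section 11 openly discloses the crossover nested in Group 2.

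**The case for a change.** The best case for a change is that the repair is cheap and the gap is specific. An exploratory outcome still needs a stated measure, and an increase in an undefined quantity cannot be judged. The TMS wording in Sections 13 and 23 leaves a reader unsure whether participants undergo any TMS procedure, which bears on what they are told at consent.

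Much of this stands as a documentation query. SICI should have been spelled out, and anyone reporting the trial will have to say what was measured and when. The TMS references do not match the second phase as described in Section 11. They are a separate inconsistency, however, because the documents never say that SICI is a TMS measure.

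What does not stand is the inference that the aim claims something the trial cannot deliver. The procedure list is visibly incomplete and the assessment battery is not itemised. The Risks to Subjects section to which Section 11 refers is not in the text available. Nor would confining Aim 3 to HRV supply a hypothesis test, since none is described for HRV either.

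**Conclusion.** No change to the plan follows. SICI is undescribed in the available text: 1 of 4 hypothesised outcomes, and 1 of the 2 in Aim 3. This is a gap in documentation within an exploratory aim, and it does not show that SICI is uncollected. Writing down a definition would supply missing detail, and deleting the word would shorten a hypothesis. Neither would alter the primary or secondary endpoint, the allocation, the visits or any planned comparison.

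The difference between 28 and 24 is 4 participants, 14.3% of enrolment. It is unexplained, but it fits ordinary over-recruitment, and an analyst would report the numbers enrolled, allocated and analysed in any case. The Aim 3 group name is a clerical slip, because the visit table identifies the group. The study-model entry is not an error.

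This conclusion assumes that the text not available does not contradict Sections 9 and 11. It also assumes that SICI, if collected, will be reported as exploratory with its measure and timing stated.

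### HRV is defined as a pre-to-post change with no analysis model or baseline adjustment named, so the default unadjusted mean change can lose precision that the pre-taVNS reading already collected could recover

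*Combined protocol and SAP*

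**What the plan says.** Section 9 (Study Endpoints) names change in HRV as the primary outcome, with the timeframe "at visits 2 and 3, Baseline (15 minutes pre taVNS application) to 15 minutes post 1 hour application of taVNS". A pre-taVNS value is therefore planned at each stimulation visit.

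Section 11 (Procedures Involved) says that HRV "will serve as the primary endpoint for response to taVNS in Aim 2". Aim 2 compares the video group with the brochures-only group, 12 versus 12 in the visit table. Aim 3 is worded as exploratory: "Explore the intended effects of taVNS in people with neuropathic pain". Its hypothesis is that "there will be a greater increase in HRV and SICI with active taVNS than with sham taVNS". It uses the 12 brochures-only participants, 6 per sequence; section 11 says that "only Group 2 will receive both active and sham taVNS in a randomized crossover design".

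On analysis, section 12 (Data Management) names SPSS and describes the quantitative analyses only as descriptive statistics. The text available names no test, regression or mixed model, and no baseline covariate. Some material between sections 17 and 19 was not available, but sections 9, 11 and 12 were.

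**The concern.** A change score with no model around it is normally summarised as a mean change per group or condition. That fixes the weight given to the pre-stimulation reading at 1. Estimating the weight from the data usually does better, apart from the small cost of estimating it.

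The issue is sharper in a crossover. Each person is already their own control, so subtracting a separate pre reading in each period brings in two more noisy measurements. With so few participants, avoidable noise in the HRV contrasts is worth removing, and the reading needed to remove it is already being collected.

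**Working it through.** The protocol gives no power calculation, standard deviation or correlation for HRV, so there is no stated figure to reproduce.

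**Inputs.** From section 11: 12 versus 12 for Aim 2; 12 people, 6 per sequence, for Aim 3. Assumed: equal pre and post variances on whichever HRV scale is used (none is named), and the correlations below.

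**Aim 2, parallel groups.** Let r be the pre-post correlation. Per person, in units of the HRV variance:
- change score: 2(1 − r)
- adjusted for the pre value: 1 − r²
- ratio, change to adjusted: 2(1 − r)/(1 − r²) = 2/(1 + r)

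Estimating the slope multiplies the adjusted variance by 1 + 1/(24 − 4) = 1.05.

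| r | 2/(1 + r) | divided by 1.05 |
|---|---|---|
| 0.5 | 1.33 | 1.27 |
| 0.7 | 1.18 | 1.12 |
| 0.8 | 1.11 | 1.06 |
| 0.9 | 1.05 | 1.00 |

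At r = 0.5, 12 per arm with adjustment performs like 12 × 1.27, or about 15, per arm without it. Break-even is at r = 2/1.05 − 1 = 0.90.

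**Aim 3, crossover.** Let w be the correlation between pre and post readings on the same day, and b the correlation between any two readings on different days. For each person take the active-minus-sham difference in post values and in pre values.
- variance of either difference: 2(1 − b)
- their correlation: r_d = (w − b)/(1 − b)
- variance of the change contrast: 4(1 − w) = 4(1 − b)(1 − r_d)
- variance after adjustment: 2(1 − b)(1 − r_d²)
- ratio, change to adjusted: 2/(1 + r_d)

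Estimating the slope with 12 people multiplies the adjusted variance by 1 + 1/(12 − 4) = 1.125.

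| w | b | r_d | 2/(1 + r_d) | divided by 1.125 |
|---|---|---|---|---|
| 0.7 | 0.7 | 0 | 2.00 | 1.78 |
| 0.7 | 0.6 | 0.25 | 1.60 | 1.42 |
| 0.8 | 0.6 | 0.50 | 1.33 | 1.19 |
| 0.9 | 0.6 | 0.75 | 1.14 | 1.02 |
| 0.95 | 0.7 | 0.83 | 1.09 | 0.97 |

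Simulation of the 6 + 6 design (20,000 trials per setting, period term fitted) gave 1.77 for the first row, 1.20 for the third, 1.01 for the fourth and 0.97 for the fifth. The second row comes from the formula only.

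Break-even is at r_d = 2/1.125 − 1 = 0.78. With b = 0.6 that is w = 0.6 + 0.78 × 0.4 = 0.91. Above it, adjustment loses slightly; the loss can never exceed the 12.5% slope cost.

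As an illustration, assume a two-sided 5% level and 80% power. The detectable crossover effect, in HRV standard deviations, is 0.98 for the change score against 0.75 adjusted at w = b = 0.7; 0.80 against 0.75 at 0.8/0.6; and 0.57 for both at 0.9/0.6.

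**The case against.** **The plan does not commit to a raw change analysis.** A reader might infer from the endpoint title that it does. The documents do not say so. Regressing the change on group plus the pre value gives the same treatment estimate as regressing the post value, so a change endpoint is compatible with adjustment. This objection stands in full: what is missing is the model, and the endpoint itself needs no correction.

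**In Aim 2 the pre-taVNS reading is not a pre-randomisation baseline.** The video is shown at visit 1 and HRV is first described at the stimulation visits. For half of Group 2 the active session is visit 3, after a sham session, whereas Group 1 has its active session at visit 2. The video or the visit order could therefore shift the pre reading. If they do, the adjusted and unadjusted contrasts estimate different quantities, and the variance ratio no longer compares like with like. This stands as a qualification. It does not favour the change score, which subtracts the same reading. Nor does it undermine Aim 3, where each pre reading precedes that session's stimulation and the order is randomised, carry-over aside.

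**The gain may be small.** True: if same-day readings track very closely, there is none. The correlations are unknown, so a loss of precision is possible but not established.

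**Conclusion.** The point holds as a gap in prespecification with a possible precision cost. Under the assumed correlations, the unadjusted change has 1.00 to 1.27 times the adjusted variance in Aim 2, and about 1.0 to 1.78 times in Aim 3. Adjustment costs at most about 5% and 12.5% in variance respectively. That asymmetry justifies adjusting, although the study remains interpretable without it.

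Three stronger readings are not supported:
- **That the change score doubles the variance.** A factor of 2 is the limiting case in which same-day readings correlate no better than readings on different days, and it ignores the cost of estimating the slope. With 12 people that case gives 1.78.
- **That the largest loss falls on the primary comparison.** Section 11 declares HRV primary for Aim 2; the crossover is the exploratory Aim 3.
- **That chance baseline imbalance is a separate bias.** With 12 per arm the chance difference has a standard deviation of √(2/12) = 0.41 HRV standard deviations. At r = 0.7, an imbalance of that size shifts the change contrast by 0.3 × 0.41 = 0.12. This shift is conditional on the imbalance observed, averages to zero under randomisation when the baseline is unaffected by allocation, and is already counted in the variance ratio.

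**What to change.** Keep the change endpoint and its measurement windows, and add a short analysis statement.

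- **Aim 3:** regress each person's active-minus-sham post difference on their active-minus-sham pre difference, with a term for sequence. With sequence coded +1/−1, the intercept is the treatment effect at zero pre difference. Using the change difference as the response gives the same treatment estimate.
- **Aim 2:** regress post-taVNS HRV (or the change) from the active session on group, with that session's pre-taVNS HRV as covariate. State that the covariate is measured after the video and that the active session falls at visit 3 for half of Group 2. Report the unadjusted change alongside as a sensitivity result.

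No new data are needed. The cost is one degree of freedom per model, and a slight loss of precision if same-day pre and post readings turn out to be very highly correlated. For Aim 2, adjustment does not remove the difference in visit timing between the groups; the wording above only makes it visible.
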